The main reason for the interim for the ongoing extension phase part 2 including all data from the main phase and extension phase up to the cut-off is to collect additional safety and efficacy data.

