Prophylactic effect of N8-GP will be concluded if the bleeding rate is significantly below 50% of the historical on-demand bleeding rate (i.e. significantly lower than 12) as well as within 25% of the historical prophylaxis bleeding rates (i.e. significantly lower than $6.8 * 1.25 = 8.5$). Since both must be met in practice it must be shown that the bleeding rate is significantly lower than 8.5.

Let AR be the true yearly bleeding rate. The null-hypothesis will be tested against the alternative hypothesis as given by:

$H_0: AR \geq 8.5$ against $H_A: AR < 8.5$

The endpoint will be analysed by a Poisson regression model on number of bleeding episodes per patient allowing for over-dispersion (using Pearson's chi-square divided by the degrees of freedom (i.e. $Scale = P_{scale}$ in SAS)) and using log observation duration as an offset. Estimates of the annualised bleeding rates will be provided with 95% confidence intervals.

For patients withdrawing prematurely, the number of bleeding episodes counting in the analysis will be imputed up to what they could be expected to have had if they had completed the trial. If e.g. a patient withdraws after 2 months with 3 bleeding episodes, but the patient should have been in the study for 12 months, then this patient will in the analysis count as having had 18 bleeding episodes in 12 months. This is similar to last observation carried forward (LOCF) and will avoid positive bias occurring from patients with many bleeding episodes withdrawing early.

The rules for calculating planned exposure time used for imputation depends on what part of the trial the patient is withdrawn from and furthermore what parts of the trial the calculations represent as described in the following.

Calculations of ABR for the Pivotal part:

Since the planned exposure time for each patient in the Pivotal phase of the trial depends on when the patient was recruited in the trial, the maximum expected exposure time based on the last visit date included in each part of the analysis will be used as planned exposure time, e.g. the date of the last patient's first visit after his 50EDs will be used for the pivotal part of the analysis where all patients should have reached at least 50 EDs (except for patients having had surgery as part of pathfinder™3).

Calculations of ABR for extension phase part 1:

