For patients who were withdrawn in the Pivotal part the planned exposure time will be until the end of the pivotal part as described above. For patients who were withdrawn in the main part after the pivotal part ended, the maximum expected exposure time will be used, i.e. 100 weeks as this is the maximum duration for main phase. For patients withdrawn during extension phase part 1, the planned exposure is 24 weeks (duration of extension phase part 1) added to the actual exposure in main

For calculations only including the randomised period, the planned exposure time will be the time from visit 14 to visit 17, i.e. 24 weeks. Patients that change from Q7D to non-randomised part of Q4D will have their bleeds imputed using a planned exposure time of 24 weeks using the same approach as in the pivotal part of the trial even though they are not withdrawn from the study. This is to avoid bias for randomized Q7D caused by patients withdrawing due to high bleeding rate.

Calculations of ABR for extension phase part 2:

For patients withdrawn prior to extension phase part 2, planned exposure is calculated as explained above. For patients withdrawing during extension phase part 2, planned exposure in extension phase part 2 will be calculated using the overall cut-date (15Aug2017) as planned end date. The actual exposure time in main and extension phase part 1 is added to the planned exposure time in extension phase part 2, to get the overall planned exposure time for a withdrawn patient.

Planned exposure time is only relevant for the treatment regimen the patient is on, when being withdrawn. Time on other regimens and time in surgery trial is subtracted when calculating planned exposure time.

For patients who withdrew within 1 month, imputation will be conducted by assuming an annualised bleeding rate of 24 (bleeds per year) for the missing period. This also applies to change from Q7D to Q4D in the randomised part of extension phase part 1.

Estimates of the annualised bleeding rates for each regimen will be provided together with the 95% confidence intervals as described in the protocol.

Sensitivity analyses:

Analysis applying a different model

A sensitivity analysis based on a negative binomial regression model with number of bleeding episodes requiring treatment as the outcome variable, and adjusting for exposure time will be performed.

Analysis without imputation to planned trial duration

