2.5 Interim Analysis

All data from the Main Phase of the trial will be analysed and reported when all patients have reached at least 50 EDs (except for patients having had surgery as part of pathfinder™3), and all patients have had their first visit after 50 EDs where all planned assessments including inhibitors have been performed. The analysis of the main phase of the trial will be based on all data up to the patient's last visit at this point. All main conclusions from the trial will be based on this reporting.

Furthermore, an interim analysis was performed when all patients had completed extension phase part 1. The interim for the extension phase part 2 will cover all data from the main phase and extension phase 1+2 up to last visit before 15-Aug-2017.

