Only treatment requiring bleeding episodes will be considered in the above evaluations of ABR. Incidence rate of FVIII-inhibitor and haemostatic effect of N8-GP when used for treatment of bleeding episodes will be evaluated based on accumulated data (Main Phase + Extension Phase part 1).

Adverse events, consumption of N8-GP, recovery and pre-dose levels will be summarised based on accumulated data (Main + Extension Phase part 1) by treatment regimen combining the every 4 day dosing regimens. In addition, separate summaries including data from part 1 only will be presented by treatment regimen for the randomised subset of patients to support the main objective of part 1 of the Extension Phase.

Other safety endpoints will be summarised based on accumulated data (Main Phase + Extension Phase part 1). Binding non-inhibitory antibodies will be listed.

PRO endpoints at end the Extension Phase part 1 will be evaluated and presented as described in section 18.9.

Data from part 2 of the Extension Phase

The main objective of extension phase part 2 is to collect long term safety and efficacy data.

ABR will be calculated as for the co-primary endpoint in the main phase, but based on the accumulated data, i.e. combined data from main phase, extension phase part 1 and extension phase part 2. Furthermore, sensitivity analyses are performed based on actual bleeding episodes and exposure times (i.e. without imputation for withdrawn patients).

Incidence rate of FVIII-inhibitor and haemostatic effect of N8-GP when used for treatment of bleeding episodes will be evaluated based on accumulated data.

Adverse events and consumption of N8-GP will be summarised based on accumulated data by treatment regimen.

Incremental recovery will be summarised by visit for extension phase part 2 and furthermore be presented graphically in the following ways:

- By N8-GP production process (extension phase part 2 data)
- According to Anti-PEG-antibody status (accumulated data)

For Anti-CHO HCP-antibodies, the number of negative/positive samples will be summarised by visit.

Other safety endpoints will be listed and/or plotted based on accumulated data.

-

PRO endpoints for extension phase part 2 will be summarised by time since first dose (since timing of visits depend on treatment regimen). Time grouping will span a year, i.e. grouping being “1 - <2 years”, “2 - <3 years”,.... The two prophylaxis regimens will be considered as a combined prophylaxis treatment regimen.

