2.11 Additional Evaluations

Exploratory analysis comparing results from study NN7008-3543, NN7008-3545, NN7008-3568 and NN7088-3776 with results from this study will be performed and reported separately. This analysis will include overall comparisons as well as individual comparisons for patients participating in one of the above listed trials and this NN7088-3859 trial, if the patient through the informed consent has given approval of such comparison of data.

3 Changes to the statistical analyses planned in the protocol

It has been clarified that treatment requiring bleeding episodes occurring in multiple locations with the same start time will be calculated as one bleed. This is in accordance to the initial setup of how data could be captured in the diary and electronic case report form (eCRF), but some changes have been made in the eCRF by mistake at a later time point where auto-query has been added to enquire all bleeding episodes which were associated with multiple locations to be captured as separate episodes.

As a conservative approach, the worst response will be used in case multiple haemostatic responses were registered for multiple bleeding locations with the same start time.

None of the non-joint bleeds will be considered as re-bleeds even if they occurred within 72 hours as the specific location is not captured in the database.

A conservative approach will be used to calculate the planned exposure time for withdrawals such that the maximum expected exposure time will be used.

An additional sensitivity analysis is added for the analysis of the ABR to investigate the robustness of the assumption that the treatment requiring bleeds can be modelled adequately using a Poisson distribution with overdispersion. The additional sensitivity analyses uses modelling based on the negative binomial distribution

It was added that ABR will be analysed when there are at least 5 patients in total and when at least one bleed was observed, in order to provide reliable estimates.

At the end of trial:

Efficacy data:

As a sensitivity analysis, analysis without imputation to planned duration will be performed. The other sensitivity analyses performed in the pivotal reporting are no longer applicable, since this was already addressed in the previous interim reportings.

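### The end-of-trial SAP imputes part 2 withdrawals only to the interim cut of 15 August 2017, which is 259 to 475 days before trial completion

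*SAP*

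**What the plan says.** SAP section 2.2.2 sets the general rule for early withdrawals: their bleeds are "imputed up to what they could be expected to have had if they had completed the trial". It then defines planned exposure separately for each part of the trial. For the pivotal part it is the "maximum expected exposure time based on the last visit date included in each part of the analysis". For patients withdrawing in extension part 2, "planned exposure in extension phase part 2 will be calculated using the overall cut-date (15Aug2017) as planned end date".

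Section 2.5 shows what that date is: the part 2 interim will "cover all data from the main phase and extension phase 1+2 up to last visit before 15-Aug-2017". Section 2 still uses the language of that interim: "The main reason for the interim for the ongoing extension phase part 2".

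For the part 2 results, section 2.10 says "ABR will be calculated as for the co-primary endpoint in the main phase, but based on the accumulated data". Section 3, which lists changes from the protocol, adds: "A conservative approach will be used to calculate the planned exposure time for withdrawals such that the maximum expected exposure time will be used". Its end-of-trial part then says: "As a sensitivity analysis, analysis without imputation to planned duration will be performed".

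In Protocol Amendment 21, section 7 (Trial Schedule), planned LPLV is 3 December 2018, and patients may complete successfully from May 2018 whatever their last scheduled visit.

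**The concern.** The SAP is marked final, is dated 14 January 2019 (after planned LPLV) and has a section on analyses at the end of the trial. Its only planned end date for part 2 withdrawals is nevertheless an interim data cut. The likely explanation is interim text carried forward. Consistent with that, the list of amendments in SAP section 1.2 does not include Amendment 21.

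The imputation is there to stop patients who bleed often and leave early from pulling the ABR down. At the end of the trial the imputed, accumulated ABR is the main long-term efficacy estimate, and the analysis without imputation is only the sensitivity analysis. SAP section 2 also excludes long-term efficacy from the conclusions already settled by the pivotal report. With the interim date kept, withdrawals before the cut are imputed for too short a period, and withdrawals after it are not imputed at all. For the second group the literal rule gives a planned exposure shorter than the observed one, and no floor is stated.

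**Working it through.** **1. The plan's own imputation example.** Imputed bleeds = observed rate × planned time. Three bleeds in 2 months with 12 months planned gives 3/2 × 12 = 18, as SAP 2.2.2 states. The result scales directly with the planned end date.

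**2. The gap.** The day in May 2018 is not given; 1 May is used.
- 15 August 2017 to 1 May 2018: 259 days
- 15 August 2017 to 3 December 2018: 475 days

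**3. Days imputed, by withdrawal date**

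| Withdrawal | End 15 Aug 2017 (SAP) | End 1 May 2018 | End 3 Dec 2018 |
|---|---|---|---|
| 15 Aug 2016 | 365 | 624 | 840 |
| 1 Jul 2017 | 45 | 304 | 520 |
| 1 Dec 2017 | none (planned end is 108 days before withdrawal) | 151 | 367 |

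**4. Effect on the accumulated ABR.** The documents give no part 2 withdrawal count, rates or exposure, so these are assumptions: N = 120 patients on one regimen, all first dosed 1 September 2012; completers bleed a = 3 times a year; k = 5, 10 or 20 part 2 withdrawals bleed at r times that rate. With an intercept-only Poisson model and log-exposure offset, the estimate is total bleeds over total time:

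ABR = [(N − k)·Tc·a + k·Tw·a·r] / [(N − k)·Tc + k·Tw]

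Tc is time from first dose to the completers' end, and Tw is time from first dose to the planned end used for withdrawals. The reference value sets Tw = Tc. Time to 15 August 2017 is 1809 days; to 1 May 2018, 1809 + 259 = 2068; to 3 December 2018, 1809 + 475 = 2284.

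Worked case, k = 10, r = 4, completers to LPLV:
- SAP rule: (110 × 2284 × 3 + 10 × 1809 × 12) / (110 × 2284 + 10 × 1809) = 970,800 / 269,330 = 3.60
- Reference: (110 × 3 + 10 × 12) / 120 = 3.75
- Difference: −3.9%

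Difference from reference under the SAP date:

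| Completers end | r | k = 5 | k = 10 | k = 20 |
|---|---|---|---|---|
| 1 May 2018 (Tw/Tc = 0.875) | 2 | −0.5% | −0.9% | −1.5% |
| | 4 | −1.3% | −2.3% | −3.6% |
| 3 Dec 2018 (Tw/Tc = 0.792) | 2 | −0.8% | −1.5% | −2.6% |
| | 4 | −2.2% | −3.9% | −6.0% |

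At r = 1 the difference is 0% throughout. Moving the assumed first dose between 1 February 2012 and 1 June 2013 widens the range for r = 2 to 4 to −0.4% to −6.8%.

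**5. Which later date** (k = 10, r = 4, reference 3.75; 17 August 2018 is the midpoint of the completion window)

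| Completers end | SAP date | 1 May 2018 | 3 Dec 2018 |
|---|---|---|---|
| 1 May 2018 | 3.66 (−2.3%) | 3.75 (0%) | 3.82 (+1.9%) |
| 17 Aug 2018 | 3.63 (−3.1%) | 3.72 (−0.9%) | 3.78 (+0.9%) |
| 3 Dec 2018 | 3.60 (−3.9%) | 3.68 (−1.7%) | 3.75 (0%) |

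The SAP date is too low in every row. LPLV is too high when completers leave early.

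**6. Wider assumptions.** A second calculation took 120 or 160 patients, mean exposure of 3.0 to 5.5 years, others bleeding at 3 or 6.8 a year, and 5 to 20 withdrawals whose time was extended by 259 or 475 days. Moving the end date changes the accumulated ABR by +0.02 to +0.43 if withdrawals bleed 12 times a year, by +0.07 to +1.00 at 24 a year, and by −0.01 to −0.10 at 1 a year.

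**The case against.** The best case on the other side accepts the dates and disputes their weight.

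- **Little depends on it.** SAP 2.10 sets no success criterion for the part 2 data, and a no-imputation analysis is planned. This stands as a limit on importance. The no-imputation analysis shows how much imputation matters, but it does not correct the date.
- **The contradiction is narrower than it looks.** The last-visit rule sits under the pivotal heading, and the maximum-exposure sentence comes before the end-of-trial part of section 3. This is fair, so those two are supporting evidence. The governing principle in 2.2.2, imputing as if the patient had completed the trial, applies to every part and is enough.
- **A floor is implied.** Section 2.2.2 speaks of a missing period, so a patient leaving after the cut has nothing to impute. That is a reasonable reading, but a final SAP should state it. Keeping observed time also reduces the effect: with all ten withdrawals on 1 December 2017 (day 1809 + 108 = 1917) and r = 4, the shortfall is 1.3% (completers to 1 May 2018) or 3.0% (to LPLV), against 2.3% and 3.9% above.
- **LPLV brings its own bias.** With k = 20, r = 4 and completers leaving on 1 May 2018, LPLV gives (100 × 2068 × 3 + 20 × 2284 × 12) / (100 × 2068 + 20 × 2284) = 4.63 against 4.50, or +2.9%. Protocol Amendment 13 also ends part 2 by country, so LPLV is not the date that every withdrawal would have reached. This stands and is the reason for a second run.
- **The pooled model is not the planned estimate.** Planned exposure applies only to the regimen at withdrawal. This stands: the effect falls on that regimen's ABR and could be larger where patients are few.

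**Conclusion.** The concern holds. As written, the rule imputes part 2 withdrawals to an interim cut, 259 days before completion opens and 475 days before planned LPLV, and it is undefined for anyone leaving after the cut. Those facts come from the documents alone.

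The size depends on assumptions. Under those of step 4 the accumulated ABR is 0.5% to 6.0% too low when withdrawals bleed at two to four times the completers' rate. It is unchanged at equal rates, and the direction reverses if withdrawals bleed less. The effect stops being small only if many withdrawals bleed at around 24 a year (step 6).

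None of the step 4 and 5 estimates comes near 8.5; the highest is the 4.63 above. These are point estimates, whereas the criterion is a confidence limit, and they depend on the assumed 3 bleeds a year. In the wider set, one extreme case (160 patients, 3.0 years, others at 6.8, 20 withdrawals at 24) moves from 8.50 to 9.32.

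The pivotal conclusions, the part 1 every-7-day conclusion (which has its own 24-week rule) and the no-imputation analysis are unaffected. This should be corrected, but it does not threaten the trial's main results.

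**What to change.** For the end-of-trial analysis:

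1. Replace 15 August 2017 with the actual LPLV date as planned end for part 2 withdrawals, in line with the SAP's maximum-exposure approach.
2. Repeat the analysis with 1 May 2018 as planned end, because LPLV gives withdrawals more weight than patients who completed from May 2018. Report both results for each regimen.
3. State that planned exposure is never less than observed exposure, and that nothing is imputed when there is no missing period.
4. Confine 15 August 2017 to the part 2 interim.

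The cost is one date and one floor in the SAP text and derivation code, plus one repeat run. No new data are needed.

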5.3.1 Prophylaxis

...

[figure not shown]
Extension Phase part 2: During this period it is possible to change the prophylaxis treatment of patients to every 4 day or 7 day treatment. For deciding to change a regimen the Investigator must monitor the patient on an on going basis and follow the below rules:

- 0-2 bleeding episodes within last 6 months on same regimen allow a less frequent dosing interval of every 7 day. Change to a less frequent treatment regimen should be done while the patient is at a site visit. *After switching, the patient must attend the next sequential a-visit in line. The a-visits are applicable to attend 2 times following a switch to every 7 day treatment regimen to allow for monthly visits the first 4 months and thereafter visits every second month while on every 7 day treatment regimen, see Table 2-3 and Figure 8-2*
- If a patient on every 7 day treatment regimen over a 8 week period experiences two or more spontaneous bleeding episodes or one severe bleeding episode requiring hospitalisation, then the patient must be switched back to every 4 day treatment regimen. *The patient must attend the next sequential visit in line and attend visits every third month while on every 4 day treatment regimen, see Table 2-3 and Figure 8-2.*

[figure not shown]
8 Methods and Assessments

...

Old figure 8-2:

New figure 8-2

OD = on-demand, PPX = prophylaxis, BE = bleeding episodes, ® = randomisation, Q4D = prophylaxis every 4 day, Q7D = prophylaxis every 7 day, w = weeks, ○ 2 consecutive a-visits are mandatory to attend upon switching to Q7D in order to achieve visits every 4 weeks (± 1 week) during the first 4 months

...

The Extension Phase part 1 will include the following visits:

- *Non-randomised prophylaxis and on-Demand patients*
Visit 14 (same date as Visit 13 (EOM)): patients are enrolled in Extension Phase
Visit 15+16: Visits at the site
 - ~~Patients in the randomised treatment arms~~ will be dosed during the visits
 - Patients on prophylaxis NOT in the randomised treatment arm will be dosed during the visits
 - Patients on the on-demand treatment arm will not be dosed during the visits
- *Randomised PPX patients*
Visit 14 (same date as Visit 13 (EOM)): patients are enrolled in Extension Phase
Visit 14a, 15, 15a +16: Visits at the site
 - Patients in the randomised treatment arms will be dosed during the visits

The Extension Phase part 2 will include the following visits:

- Visit 17-n** : Visit at site

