To investigate the effect over time the bleeding rates per month will be calculated and summarised numerically and graphically. This will be done by treatment regimen and only including the first consecutive period on each treatment regimen. A patient that is on different treatment regimens during the trial will therefore have bleeding rate per month calculated for each treatment regimen, but only including the first consecutive period on each treatment regimen. Surgery leave is not considered change in treatment regimen.

Similarly the bleeding rate by calendar month will be calculated and presented. If there is a calendar effect it is conceivable that it would be reversed in the southern hemisphere compared to the

northern. Therefore, calendar months for Australia and Brazil are shifted 6 months, i.e. January is changed to July, February to August etc.

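### The accumulated every-7-day ABR is an on-regimen rate cut short by forced returns for bleeding; it should be labelled so, with the negative binomial analysis explicitly kept beside it

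*SAP*

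**What the plan says.** **Return rule.** Protocol 5.3.1 (Extension Phase part 2, Amendment 15) lets a patient move to every-7-day dosing after 0–2 bleeds in 6 months. If that patient, within 8 weeks, "experiences two or more spontaneous bleeding episodes or one severe bleeding episode requiring hospitalisation, then the patient must be switched back" to every 4 days.

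**Part 1.** SAP 2.2.2 imputes the bleeds of randomised patients who leave every-7-day dosing up to 24 weeks, and gives the reason: "This is to avoid bias for randomized Q7D caused by patients withdrawing due to high bleeding rate".

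**Part 2.** SAP 2.2.2 describes imputation only for patients withdrawn from the trial: "Planned exposure time is only relevant for the treatment regimen the patient is on, when being withdrawn". Time on other regimens is subtracted. It then adds: "Estimates of the annualised bleeding rates for each regimen will be provided together with the 95% confidence intervals as described in the protocol". SAP 2.10 bases the part 2 ABR on accumulated data, and SAP 3 drops ABRs restricted to part 2.

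**Sensitivity analyses.** SAP 2.2.2 lists "A sensitivity analysis based on a negative binomial regression model with number of bleeding episodes requiring treatment as the outcome variable". For end of trial, SAP 3 names only the analysis without imputation and continues: "The other sensitivity analyses performed in the pivotal reporting are no longer applicable, since this was already addressed in the previous interim reportings".

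**The concern.** Every-7-day time ends because of the outcome being measured. High bleeders are returned early and contribute little time; low bleeders stay and contribute a lot. A Poisson rate of total bleeds over total time therefore weights towards low bleeders. The SAP calls this mechanism a bias in part 1 but carries no correction into part 2. The no-imputation analysis does not help, because returned patients had nothing imputed for every-7-day dosing in the first place.

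The error is in the favourable direction, on a risk that Protocol 3.1.4 (Amendment 14) names itself: more break-through bleeding after moving to every 7 days. SAP 2 excludes conclusions on every-7-day and long-term prophylaxis from the pivotal report, so readers will look to the later reports for them.

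**Working it through.** **1. The plan's own figure.** The documents give no figure for the accumulated ABR by regimen. The planning inputs can be checked through the stated power (Protocol 18.1, Amendment 6: effective ABR 7.0, over-dispersion 5, 120 patients, limit 8.5, one-sided 2.5%): Φ((8.5 − 7.0)/√(7.0 × 5/120) − 1.96) = Φ(1.5/0.540 − 1.96) = Φ(0.82) = 79%, as stated.

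**2. From over-dispersion to spread between patients.** Protocol 18.5 (Amendment 6) attributes the over-dispersion mainly to patients bleeding at different rates. With gamma-distributed rates of mean m and shape a, the one-year over-dispersion is 1 + m/a. For m = 6.8 and over-dispersion 5, a = 6.8/4 = 1.7.

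**3. Hand check.** Take one patient at 6 bleeds/year and one at 2/year, all bleeds spontaneous, no re-entry, follow-up cut at 2.75 years.
- At 6/year, the chance that a gap is within 56 days is 1 − exp(−6 × 56/365.25) = 0.60. Return comes after 1 + 1/0.60 = 2.66 bleeds on average, in 2.66/6 = 0.44 years.
- At 2/year, simulation gives 1.66 years on regimen, so 2 × 1.66 = 3.3 bleeds.
- Pooled rate: (2.66 + 3.3)/(0.44 + 1.66) = 2.85, against a true mean of 4.0.

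**4. Simulation.** From the documents: ABR 6.8, shape 1.7, entry with 0–2 bleeds in 6 months (entrants' mean 3.6/year), return at a second spontaneous bleed within 56 days, re-entry after 6 months with 0–2 bleeds. Assumed: spontaneous share 50–100%, 2.75 years on study, rule always followed, every-7-day rate 1, 1.5 or 2 times the every-4-day rate. Settings with half or more returned by 24 weeks are left out, because Protocol 5.3.1 (Amendment 14) would close the arm.

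| Rate ratio | Spontaneous share | True mean | Poisson ABR, re-entry from 24 weeks | Poisson ABR, re-entry from 36 weeks |
|---|---|---|---|---|
| 1 | 50% | 3.6 | 3.10 (14% low) | 3.06 (15% low) |
| 1 | 75% | 3.6 | 2.92 (19% low) | 2.82 (22% low) |
| 1 | 100% | 3.6 | 2.75 (24% low) | 2.68 (26% low) |
| 1.5 | 50% | 5.4 | 4.33 (20% low) | 4.27 (21% low) |
| 1.5 | 75% | 5.4 | 4.07 (25% low) | 3.95 (27% low) |
| 2 | 50% | 7.2 | 5.54 (23% low) | 5.35 (26% low) |

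With no difference between patients the bias is zero, which confirms the mechanism. With rate ratio 1 and no re-entry it grows from 5–12% at 24 weeks to 11–22% at 1 year and 22–37% at 2.75 years.

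**5. Milder settings** (rate ratio 1, re-entry from 24 weeks).
- 30% of bleeds spontaneous: 9% low at ABR 6.8, 6% at ABR 4.
- Return only after more than two spontaneous bleeds, as SAP 1.1 words the rule, half spontaneous: 7% low at ABR 6.8, 4% at ABR 4.
- ABR 4 with half spontaneous: about 10% low.
- Stacking ABR 4, 30% spontaneous and less spread (shape 4): 3% low.

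**6. Negative binomial on the same data** (log observed-time offset, one row per patient). Return depends only on recorded bleeds, so under a patient-level rate the stopping does not distort the likelihood. Without re-entry the mean is within 4% of the truth. With re-entry at ABR 6.8 it is 3–6% low. A joint fit forcing one dispersion on both regimens runs 4–5% high.

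**7. CI coverage**, five of the six settings of step 4 (all but rate ratio 1 with 100% spontaneous), with 40 or 80 every-7-day patients assumed. The Poisson 95% CI covers the true mean in 34–73% or 4–53% of trials; the negative binomial CI covers it in 93–95%.

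**The case against.** **The Poisson rate is a valid quantity.** It is the rate while on every-7-day dosing under a mandatory return rule, and that rule is part of the regimen as studied. This stands. It makes labelling part of the remedy, but the figure is still not the mean rate of patients placed on the regimen, which is how an unlabelled ABR would be read.

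**The by-regimen accumulated estimate is inferred.** SAP 2.10 does not say by regimen for the ABR, although it does for adverse events. Protocol 18.10 describes an accumulated ABR for the every-4-day regimens combined. SAP 2.2.2, with its rules for time on other regimens and its promise of estimates per regimen, makes the by-regimen reading the better one, but it is not explicit.

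**A reader might infer that the SAP drops the negative binomial analysis.** The documents do not establish that. SAP 3 retires analyses done in the pivotal reporting, and nothing shows that this one was among them. SAP 2.2.2 says it will be performed, and where that section retires an analysis (the 12-month one) it says so on the spot. The fair charge is ambiguity. Nor would that analysis necessarily recover the mean as written: the SAP says only that exposure time is adjusted for. It specifies no log-time offset, no row per regimen and no removal of imputation.

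**The pattern is partly visible already.** Monthly rates are planned: "This will be done by treatment regimen and only including the first consecutive period on each treatment regimen". They help only in part. At rate ratio 2 and half spontaneous, the monthly rate falls from 7.0 in month 1 to 4.2 in month 12 although no patient's rate changes, which could pass for improvement. With 40 patients and a true rate of 5.4, the month-1 rate spans 2.7–8.4 in 95% of trials. Protocol 18.10 also plans a summary of frequency and time on each regimen, which SAP 3 does not list as removed.

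**Compliance.** Protocol 5.3.1 lets clinical judgement override the rule. If it is followed half the time, the bias is 11% (rate ratio 1, half spontaneous, re-entry).

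**Conclusion.** The point holds for supportive long-term data. On the better reading of SAP 2.2.2 and 2.10, the accumulated every-7-day Poisson ABR lies below the mean rate of patients placed on that regimen. It is about 14–27% low under the planning values with re-entry, at least half of bleeds spontaneous and the rule always followed, and about 4–10% low in the milder settings of step 5. The reason given in SAP 3, that earlier reports already dealt with the other analyses, does not cover this: the pivotal part had no returns from every 7 days, part 1 lasted 24 weeks, and the bias grows with follow-up.

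Two stronger conclusions may tempt a reader. The first is that the every-7-day efficacy conclusion is undermined. It is not: the test against 8.5 belongs to the randomised part 1 analysis, which imputes for patients who return, and part 2 has no test. The second is that the CI will generally fail badly. Coverage falls below 95%, but by how much depends on the assumed spontaneous share, follow-up, compliance with the rule and number of patients, none of which the documents give.

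**What to change.** In SAP 2.10 and SAP 3:

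1. State that the negative binomial analysis is run at end of trial for the accumulated ABR by regimen: log observed-time offset, one row per patient per regimen, separate dispersion (or a separate fit) per regimen, no imputation. Show it beside the Poisson result.
2. Label the Poisson every-7-day ABR as an on-regimen rate under a forced-return rule, and note under the monthly rates that a fall over time may reflect high bleeders leaving.
3. Report returns from every 7 to every 4 days by recorded reason (collected under Protocol 8.1.4), and re-entries, alongside the regimen summary planned in Protocol 18.10.

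Do not extend the part 1 imputation over several years: in simulations without re-entry over 3 years it overcorrects by 23–66%.

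The cost is one SAP paragraph, one model run and one count table, all on data already collected. The every-7-day figure becomes less favourable, and with re-entry the negative binomial mean may still be up to about 6% low. The part 1 analysis is unchanged.
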